7.5 Subgroup Definitions

The following subgroups will be explored for key safety analyses:

- Gender
- Age ($<65, \ge 65, \ge 65$ to $<75, \ge 75$)
- Race (white, non-white)
- Baseline renal function (estimated GRF \leq 60 or estimated GFR \geq 60)
- Weight (< or \ge median)
- Baseline MAO-B inhibitor medications (Yes, No)
- Baseline Dopamine Agonist medications (Yes, No)
- Baseline levodopa dose (< or ≥ median)
- Time since PD diagnosis in years (< or \ge median)
- Age at PD diagnosis (< or \ge median)
- Prior Deep Brain Stimulation (Yes, No)
- Geographic Region (European Union vs North American)

For subgroups categorizations based on median values, a value for each treatment/analysis group will be calculated and subjects will be categorized separately for each treatment/analysis group in which they are included.

7.6 Definitions of Baseline, Analysis Day 1, and Study Day 1

The baseline assessment will be the last available assessment prior to the first dose of study medication for a particular treatment. For subjects receiving multiple treatments, baseline assessments will be defined for each treatment assignment. For subjects receiving 340 mg ADS-5102 in more than one study, the following logic will be applied to assign the baseline value:

- For subjects continuing into ADS-AMT-PD302 with no gap in treatment prior to enrollment, the baseline assessment will be the last available assessment prior to the first dose of 340 mg ADS-5102 in any study.
- For subjects continuing in ADS-AMT-PD302 with a gap in treatment prior to enrollment, the baseline assessment will be the last available assessment prior to the first dose of 340 mg ADS-5102 in ADS-AMT-PD302. Assessments from the first study in which the subject enrolled will not be considered for assignment as baseline.

An overall baseline value will be determined and used in summaries were overall values are calculated and displayed. This value will be assigned following the same logic outlined previously, but study treatment will not be considered in the selection of this value.

Analysis Day 1 is defined as the date of the baseline visit. Subjects should be dispensed the study drug at the baseline visit and presumably take the first dose at bedtime on the same day. No Day 0 is defined. Negative study days indicate observations were obtained prior to treatment.

Study Day 1 is defined as the date of the first dose of study drug for the individual study in which the subject participated.

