7.7 Calculations Using Dates

The following conventions will be used to calculate analysis day for reporting purposes:

- Analysis Day = date of measurement analysis day 1 +1, if date of measurement is on or after analysis day 1.
- Analysis Day = date of measurement analysis day 1, if date of measurement is prior to analysis day 1.

Study day will be presented in applicable listings where the calculated analysis day of the measurement is negative due to the definition of baseline for rollover subjects with treatment gaps prior to enrollment in the open-label extension. The following conventions will be used to calculate study day for reporting purposes:

- Study Day = date of measurement study day 1 +1, if date of measurement is on or after study day 1.
- Study Day = date of measurement study day 1, if date of measurement is prior to study day 1.

8 Summary Population

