8.1 Disposition of Subjects

Disposition data from each study will be integrated, listed, and summarized for the Safety population.

A frequency table by treatment/analysis group and overall will include the number and percentage of subjects along with last available completion status.

A separate table will show the number (%) of subjects who withdrew and the primary reason for withdrawal, by treatment/analysis group and overall. The primary reasons of withdrawal reported by subjects will be presented in this table. The number (%) of subjects who discontinued study drug and the reason for early discontinuation will be summarized in a

separate table. Subjects may contribute more than one event to the summary table since it is possible for a subject to discontinue from more than one study. A footnote indicating the number of subjects with multiple study discontinuations will be included in the summary table.

The time to discontinuation of study drug will be analyzed. The time to discontinuation is defined as the number of days from the Analysis Day 1 date to the last dose of study drug for a particular treatment. Subjects will be censored if no early study drug discontinuation occurred. The median duration and the associated 95% confidence interval for each treatment group will be estimated using the Kaplan-Meier method (log-log transformation). Kaplan-Meier estimates of the survival function will be calculated and displayed graphically.

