8.8 Treatment Compliance

Treatment compliance data will not be integrated. Summaries are provided in the individual study results.

9 Safety Analysis

Safety endpoints will be summarized using integrated data by treatment/analysis group from the time of first dose and include all available safety data. No formal statistical testing is planned.

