9.1 Study Drug Exposure

Study drug exposure data will be integrated, listed, and summarized for the Safety population.

Duration of exposure will be summarized by treatment/analysis group and is defined as:

Duration of exposure (Days) = (Date of Last Dose – Analysis Day 1) + 1.

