PREFERRED TERM #1	xx (xx.x)				
PREFERRED TERM #2	xx (xx.x)				

Note: Subjects may have more than one medication per ATC level category and preferred term. At each level of subject summarization, a subject is counted once if the subject reported one or more medications. Concomitant medications were coded with the WHO Drug dictionary dated March, 2014. PD medications are medications indicated by the investigator as prescribed for PD and are classified as Anti-Parkinson Drugs.

Source Data: Listing 2.4

Table 1.4.4
Concomitant Non-PD Medications
Safety Population

ATC LEVEL 1 ATC LEVEL 2 PREFERRED TERM	Placebo (N=xx) n (%)	340mg ADS-5102 (N=xx) n (%)	≥340mg ADS-5102 (N=xx) n (%)	ADS-5102 (N=xx) n (%)	All (N=xx) n (%)
Number (%) of subjects with any Non-PD concomitant medication	xx (xx.x)	xx (xx.x)	xx (xx.x)	xx (xx.x)	xx (xx.x)
ATC LEVEL 1 #1	xx (xx.x)	xx (xx.x)	xx (xx.x)	xx (xx.x)	xx (xx.x)
ATC LEVEL 2 #1	xx (xx.x)	xx (xx.x)	xx (xx.x)	xx (xx.x)	xx (xx.x)
PREFERRED TERM #1	xx (xx.x)	xx (xx.x)	xx (xx.x)	xx (xx.x)	xx (xx.x)
PREFERRED TERM #2	xx (xx.x)	xx (xx.x)	xx (xx.x)	xx (xx.x)	xx (xx.x)
PREFERRED TERM #3	xx (xx.x)	xx (xx.x)	xx (xx.x)	xx (xx.x)	xx (xx.x)
PREFERRED TERM #4	xx (xx.x)	xx (xx.x)	xx (xx.x)	xx (xx.x)	xx (xx.x)

Note: Subjects may have more than one medication per ATC level category and preferred term. At each level of subject summarization, a subject is counted once if the subject reported one or more medications. Concomitant medications were coded with the WHO Drug dictionary dated March, 2014. Non-PD medications are medications indicated by the investigator as prescribed for non-PD related treatment. Anti-Parkinson Drugs may be listed if taken for a non-PD indication.

Source Data: Listing 2.4

Table 1.5
Study Drug Duration of Exposure
Safety Population

	Placebo (N=xx)	340mg ADS-5102 (N=xx)	≥340mg ADS-5102 (N=xx)	ADS-5102 (N=xx)
Study drug duration of exposure (days)				
n	XX	XX	xx	XX
Mean	XX.X	XX.X	XX.X	XX.X
SD	XX.XX	xx.xx	XX.XX	XX.XX
Median	XX.X	XX.X	xx.x	XX.X
Min, Max	XX, XX	XX, XX	xx, xx	xx, xx

Note: Treatment duration is defined as (Last dose date - First dose date) + 1. For subjects with a gap in treatment prior to enrolling in ADS-AMT-PD302, only data from ADS-AMT-PD302 is used.

Source Data: Listing 2.1.3

Table 1.6.1.1
Overview of Adverse Events
Safety Population

		340mg	≥340mg	
	Placebo	ADS-5102	ADS-5102	ADS-5102
	(N=xx)	(N=xx)	(N=xx)	(N=xx)
	n (응)	n (%)	n (%)	n (%)
Number (%) of subjects with any:				

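### For subjects who re-enter after a treatment gap, the exposure table covers only PD302 while adverse events and discontinuation counts cover both courses

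*SAP*

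**What the plan says.** **Exposure.** SAP 9.1 opens its formula with "Duration of exposure (Days) = (Date of Last Dose", then subtracts Analysis Day 1 and adds one day. The note to Table 1.5 adds, for re-entrants: "For subjects with a gap in treatment prior to enrolling in ADS-AMT-PD302, only data from ADS-AMT-PD302 is used".

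**Baseline and clock.** SAP 7.6 introduces its special logic with "For subjects receiving 340 mg ADS-5102 in more than one study, the following logic will be applied to assign the baseline value". Where there was a gap, baseline comes from PD302: "Assessments from the first study in which the subject enrolled will not be considered for assignment as baseline". Also in 7.6, "Analysis Day 1 is defined as the date of the baseline visit". Where there was no gap, baseline is taken before the first 340 mg dose in any study, so those subjects keep both periods of dosing.

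**Discontinuation.** SAP 8.1: "The time to discontinuation is defined as the number of days from the Analysis Day 1 date to the last dose of study drug", taken for a particular treatment. The same section, and the note to Table 1.1.2, let a subject contribute an event from each study.

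**Adverse events.** SAP 9 summarizes safety "from the time of first dose and include all available safety data". SAP 9.2 treats every event on the adverse event page as treatment-emergent. Neither the text nor any adverse event shell limits gap subjects to PD302.

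**First-course records.** SAP 7.7 expects them to remain: "Study day will be presented in applicable listings where the calculated analysis day of the measurement is negative due to the definition of baseline".

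**The concern.** A Group 2 subject in the protocol can have two courses of study drug separated by time off drug. Leaving the off-drug time out of exposure is sensible. The plan goes further and leaves out the whole first course, while the events that arose during that course stay in the incidence tables. The same 340 mg column then reports events from two courses and dosing days from one.

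This is the integrated safety summary for a submission, and duration of exposure is what a reader uses to judge how much experience lies behind an incidence. Subjects who rolled over without a gap have both periods counted, so the exposure column also mixes two definitions. In the time-to-event outputs, a first-course stop can appear in Table 1.1.2 with no matching time in Table 1.1.3, and re-entrants who completed an earlier study start again at day 1.

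**Working it through.** The documents give no exposure total, so there is no figure to reproduce. The check is to trace the rules and then do day arithmetic.

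**Which course each output covers, for a subject given 340 mg in two studies with a gap**

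| Output | Governing text | Course covered |
|---|---|---|
| Exposure, Table 1.5 | Table note; SAP 9.1 with 7.6 | PD302 only |
| Discontinuation curve, Table 1.1.3 | SAP 8.1 with 7.6 | PD302 only |
| Discontinuation counts, Table 1.1.2 | SAP 8.1; table note | Both |
| Adverse event incidence | SAP 9, 9.2 | Both |
| Onset curves | SAP 9.2.8 counts from first dose; figure notes count from Analysis Day 1 | Not settled |

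**Inputs**
- First course: AM201 8 weeks = 56 days; PD301 25 weeks = 175 days (SAP 3).
- Maximum PD302 treatment: 101 weeks = 707 days (Protocol 11.2).
- PD302 days accrued at the database freeze: not given, so 90 to 707 is assumed. For orientation, the protocol puts study start at 14 July 2014 and the SAP is dated 13 November 2015. That is 488 days counting both ends.

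**Share of on-drug time dropped** = first course ÷ (first course + PD302 days)

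| PD302 days (assumed) | AM201 first course | PD301 first course |
|---|---|---|
| 90 | 56/146 = 38.4% | 175/265 = 66.0% |
| 180 | 56/236 = 23.7% | 175/355 = 49.3% |
| 365 | 56/421 = 13.3% | 175/540 = 32.4% |
| 488 | 56/544 = 10.3% | 175/663 = 26.4% |
| 707 | 56/763 = 7.3% | 175/882 = 19.8% |

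True on-drug time divided by Table 1.5 time, for such a subject, is 763/707 = 1.08 to 146/90 = 1.62 (AM201) or 882/707 = 1.25 to 265/90 = 2.94 (PD301).

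**One worked subject (all values assumed).** The first course is 56 days at 340 mg with an event on day 20, followed by a 365-day gap and 200 days in PD302.
- Table 1.5 exposure is 200 days. Both courses sum to 56 + 200 = 256.
- Counting from the first course's day 1, PD302 Analysis Day 1 is day 56 + 365 + 1 = 422. By SAP 7.7 the event falls on analysis day 20 − 422 = −402, although its study day is 20.
- The event counts in the 340 mg incidence table, but it cannot be placed on an onset axis that starts at Analysis Day 1. If onset is instead counted from the first course's first dose, a later event carries 365 off-drug days as time at risk.

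**Totals.** The number of gap subjects is not stated. If 5 to 21 AM201 subjects re-entered (21 is about one quarter of 83), 5 × 56 = 280 to 21 × 56 = 1,176 days are dropped, or 0.8 to 3.2 person-years.

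**Placebo, on a literal reading of the note.** AM201 had 83 − 61 = 22 placebo subjects (Protocol 4.4) and PD301 had 126/2 = 63. If all 22 re-entered after a gap, 22 × 8 = 176 of 176 + 63 × 25 = 1,751 planned placebo subject-weeks would go, or 10.1%. This is a ceiling for AM201, not an estimate.

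**The case against.** Several stronger readings are tempting, and the documents do not support them.

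- **Biased rates.** A reader might infer that event rates per unit of exposure are inflated. Adverse event percentages use subject counts (SAP 9.2), and no exposure-adjusted rate is planned. The planned percentages are unaffected.
- **All gap subjects reset.** The 7.6 logic is written for 340 mg in more than one study. Otherwise baseline is set per treatment, so a former placebo subject keeps a placebo clock. For 260 or 420 mg followed by 340 mg, the clock in the pooled columns is not spelled out. The Table 1.5 note has no such limit.
- **Negative discontinuation times.** These do not arise. The clock runs to the last dose of that treatment, which for a repeat 340 mg subject is in PD302. First-course stops should also be few, because Group 2 must have completed earlier study visits and excludes those who stopped for related intolerable events. They remain possible, since subjects who stopped drug were encouraged to complete assessments (Table 1.1.2 footnote).
- **Invalid change from baseline.** The laboratory and vital-sign footnotes speak of post-baseline values, which a first-course value is not when baseline is at PD302. What remains is an ambiguity. The on-treatment extremes in SAP 9.3 and the worst on-study values in the shift tables have no gap restriction.
- **Contradictory day labels.** SAP 7.7 concerns negative analysis days and shows study day in the listings. Study day is counted within each study, so first-course study days are positive.

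Three further points are fair. No sentence says specifically that first-course events of gap subjects are kept; this follows from the general rules and from 7.7. PD301 gap subjects are permitted but not shown to exist, and direct rollover was available to PD301 completers. The data are not lost, because Listing 2.1.3 holds dose dates by study.

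None of this removes the central inconsistency. The stated exposure rule drops a course whose events the stated event rules keep.

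**Conclusion.** The point holds as a mismatch between outputs. For gap subjects, Table 1.5 understates exposure by up to 56 days (AM201) or 175 days (PD301) each. The understated share is about 7% to 38% or 20% to 66% of the subject's on-drug time over the assumed range of PD302 duration. The effect on column totals cannot be stated, because neither the number of gap subjects nor the freeze date is given.

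The clock reset is explicit only for repeat 340 mg subjects. The loss of placebo exposure depends on reading the Table 1.5 note literally: PD302 has no placebo arm, so a placebo subject with a gap would have nothing left to count. The onset, laboratory and vital-sign parts are unsettled rules, not demonstrated errors. This should be corrected before the integrated tables are produced. It is not a reason to distrust the incidence percentages.

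**What to change.** Delete the gap sentence from the Table 1.5 note. In SAP 9.1 and Table 1.5, define exposure for each treatment/analysis group as the sum over courses of (last dose − first dose + 1), with the gap excluded.

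Then carry one course-based rule through the other outputs:
- State which course or courses Table 1.1.2, Table 1.1.3 and the onset curves count from, so that events and time at risk cover the same courses and off-drug time is never at risk. Settle the 9.2.8 and figure-note definitions at the same time. Ending gap subjects' curves at the first course while exposure counts both would create a new mismatch and lose their PD302 retention.
- Compare each on-treatment laboratory or vital-sign extreme, including in the shift tables, only with the baseline of its own course. Because SAP 7.2 allows a subject once per group, say which course supplies that entry.
- Say how the pooled columns treat subjects whose earlier dose was 260 or 420 mg.

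The cost is SAP wording and one extra derivation per course. First and last dose dates by study are already planned for Listing 2.1.3, and no new data are needed.

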5.1 Safety

The Safety population will include all subjects who received at least one dose of study drug. It will be used for all safety analyses.

6 General Considerations for Statistical Analyses

Analysis Dataset Model (ADaM) datasets will be in accordance with the Clinical Data Interchange Standards Consortium (CDISC) standards and will be derived from the individual study data tabulation model (SDTM) and ADaM datasets for each study.

All tables, listings, figures and any other supportive SAS output will include in the footer explanatory notes that will indicate, at a minimum, the programming source (i.e., name, file path of the SAS program that generates the output), and run date.

Continuous data will be described using descriptive statistics as follows: number of observations (n), mean, median, standard deviation, minimum, and maximum, unless otherwise specified. All minimum and maximum values will be displayed with the same number of decimal places relative to the raw data, the mean and median will be displayed with one additional decimal place, and the standard deviation will be displayed with two additional decimal places.

Categorical data will be summarized by the number and percentage of subjects in each category. The denominator of all percentages will be the number of subjects in the population of interest, unless otherwise stated. When count data are presented, the percent will be suppressed when the count is zero in order to draw attention to the non-zero counts. A row denoted "Missing" will be included in count tabulations where necessary to account for dropouts and missing values. Non-zero percentages will be rounded to one decimal place, except 100% will be displayed without any decimal places.

In summary tables for categorical data, all categories will be presented if they are specified on the Case Report Form (CRF), or if categories are ordered intervals (e.g., age groups), regardless of whether data were present in each category, unless otherwise specified. For other categorical data (e.g., AEs and medications), only categories with non-zero frequencies will be presented.

Data will be displayed in all listings sorted by subject, study ID, and treatment. All summaries will be presented by treatment/analysis group, unless otherwise specified.

When no data are available for a table or appendix, an empty page with the title will be produced with suitable text (e.g., "There are no observations for this table/appendix.").

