9.2 Adverse Events

An adverse event (AE) is any untoward medical occurrence that occurs in conjunction with the use of a medicinal product in humans, whether or not considered to have a causal relationship to the medicinal product. An AE can, therefore, be any unfavorable or unintended sign (including a clinically significant abnormal laboratory finding), symptom, or disease

temporally associated with the use of a medicinal product, whether or not considered related to the medicinal product.

Adverse event data will be integrated, listed, and summarized for the Safety population. Events will be presented according to MedDRA® system organ class (SOC) and preferred term (PT). Summaries will be ordered alphabetically by SOC and PT, and by decreasing frequency of preferred term among all treatment/analysis groups regardless of whether a "total" column is presented.

Partial (Incomplete) AE onset and end dates will be listed as such. All AEs collected on the AE eCRF page will be considered treatment–emergent.

Most commonly reported (at least 2% of either active or placebo treatments) AEs will be presented by preferred term, and summarized by treatment/analysis group.

For each summary, at each of the SOC and PT levels, a subject will be counted once if he/she reported one or more AEs. Percentages will be calculated out of the number of subjects in the Safety population.

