9.2.8 Adverse Events of Special Interest

Adverse events of special interest are grouped into three event categories: Neuropsychiatric (CNS), Falls, and Hallucinations. The CNS category combines the following SOCs: Nervous system disorder and Psychiatric disorder. The Falls category combines all PTs that contain the term "Fall" or "Falls". The Hallucinations category combines all PTs that contain the term "Hallucination".

Event incidence will be summarized treatment/analysis group.

Time to onset will be analyzed and is defined as the number of days from the first dose of study drug to the onset of the first AE in the category. Subjects will be censored at the latest date known not to have had such AE. The median time to event and the associated 95% confidence interval for the Placebo and 340 mg ADS-5102 treatment groups will be estimated using the Kaplan-Meier method. Kaplan-Meier estimates of the survival function will be calculated and displayed graphically.

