xxxxx-xx-xxx	XXXXX	340mg ADS-5102	XXXXXXXXXXXXXXXXXXXXXXXXXXXXXXXXXXXXXX	DDMMMYYYY (xx)/ DDMMMYYYY (xx)/ XX	Moderate/ Related/ Recovered/Resolved with sequelae/ Drug Interrupted
xxxxx-xx-xxx	XXXXX	340mg ADS-5102	XXXXXXXXXXXXXXXXXXXXXXXXXXXXXXXXXXXXXX	DDMMMYYYY (xx)/ DDMMMYYYY (xx)/ XX	Severe/ Not Related/ Unknown/ Drug Withdrawn
xxxxx-xx-xxx	XXXXX	260mg ADS-5102	XXXXXXXXXXXXXXXXX/ XXXXXXXXXXXXXXXX/ XXXXXX	DDMMMYYYY (xx)/ DDMMMYYYY (xx)/ XX	Mild/ Related/ Not Recovered/Not resolved/ Other
XXXXX-XX-XXX	XXXXX	340mg ADS-5102	XXXXXXXXXXXXXXXXXXXXXXXXXXXXXXXXXXXXXX	DDMMMYYYY (xx)/ DDMMMYYYY (xx)/ XX	Severe/ Not Related/ Fatal/ Dose not changed

¹Duration (Days) = Stop date - Start date + 1.

Source Data: Listing 2.6.1

<DIRECTORY PATH>PROGRAM NAME Executed: DDMMMYYYY hh:mm

Adverse Events Leading to Study Drug Discontinuation, by System Organ Class and Preferred Term Safety Population

Same display as 1.6.2.1

Note: A subject is counted once within each preferred term and system organ class. Percentages are calculated out of the number of subjects in each treatment/analysis group. AEs are coded using MedDRA Version 17.0.

Source Data: Listing 2.6.3

<DIRECTORY PATH>PROGRAM NAME Executed: DDMMMYYYY hh:mm

Table 1.6.8

Adverse Events Leading to Study Drug Dose Reduction, by System Organ Class and Preferred Term Safety Population

Same display as 1.6.2.1

Note: A subject is counted once within each preferred term and system organ class. Percentages are calculated out of the number of subjects in each treatment/analysis group. AEs are coded using MedDRA Version 17.0.

Source Data: Listing 2.6.3

Table 1.6.9 Listing of Adverse Events Leading to Death Safety Population

Same display as 1.6.6, with outcome "Death".

¹Dur = Duration (Days = Stop date - Start date + 1). Source Data: Listing 2.6.1

Table 1.6.10.1
Incidence of AE (Neuropsychiatric)
Safety Population

System Organ Class		340mg	≥340mg	
Preferred Term	Placebo	ADS-5102	ADS-5102	ADS-5102
Number of AE (Neuropsychiatric) events	XX	XX	XX	XX
System Organ Class 1	XX	XX	XX	XX
Preferred Term 1	xx	XX	XX	XX
Preferred Term 2	xx	XX	XX	XX
Preferred Term 3	xx	XX	XX	XX
	XX	XX	XX	XX
	xx	XX	XX	XX
System Organ Class 2	xx	XX	XX	XX
Preferred Term 1	xx	XX	XX	XX
Preferred Term 2	XX	XX	XX	XX
Preferred Term 3	xx	XX	XX	XX

Note: The Neuropsychiatric category combines the following System Organ Classes: Nervous system disorder and Psychiatric disorder. AEs are coded using MedDRA Version 17.0.

Source Data: Listing 2.6.1

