Kaplan-Meier Analysis of Time to Onset of AE (Neuropsychiatric) by Geographic Region Safety Population

Repeat of 1.6.10.3

Geographic Region:

- 1. European Union
- 2. North America

Note: Percentages are calculated out of the number of subjects in each treatment group. "+" in MIN - MAX means censored value. AEs are coded using MedDRA Version 17.0. NE = Non-estimable.

Note: The Neuropsychiatric category combines the following System of Organs: Nervous system disorder and Psychiatric disorder. Subjects will be censored at their last contact date if no AE (Neuropsychiatric) occurred.

Source Data: Listing 2.6.1

Table 1.6.11.1
Incidence of AE (Falls)
Safety Population

Repeat of 1.6.10.1

Note: Percentages are calculated out of the number of subjects in each treatment group. "+" in MIN - MAX means censored value. AEs are coded using MedDRA Version 17.0. NE = Non-estimable.

Note: The Falls category combines all Preferred Terms that contain the terms "Fall" or "Falls". Subjects will be censored at their last contact date if no AE (Falls) occurred.

Source Data: Listing 2.6.1

<DIRECTORY PATH>PROGRAM NAME Executed: DDMMMYYYY hh:mm

Table 1.6.11.2

Kaplan-Meier Analysis of Time to Onset of AE (Falls)

Safety Population

Repeat of 1.6.10.2

Note: Percentages are calculated out of the number of subjects in each treatment group. "+" in MIN - MAX means censored value. AEs are coded using MedDRA Version 17.0. NE = Non-estimable.

Note: The Falls category combines all Preferred Terms that contain the terms "Fall" or "Falls". Subjects will be censored at their last contact date if no AE (Falls) occurred.

Source Data: Listing 2.6.1

<DIRECTORY PATH>PROGRAM NAME Executed: DDMMMYYYY hh:mm

Programming Note: Some percentiles will be non-estimable. When this occurs, use " $NE^{1/7}$

Kaplan-Meier Analysis of Time to Onset of AE (Falls) by Gender Safety Population

Repeat of 1.6.10.3

Gender:

- 1. Female
- 2. Male

Note: Percentages are calculated out of the number of subjects in each treatment group. "+" in MIN - MAX means censored value. AEs are coded using MedDRA Version 17.0. NE = Non-estimable.

Note: The Falls category combines all Preferred Terms that contain the terms "Fall" or "Falls". Subjects will be censored at their last contact date if no AE (Falls) occurred.

Source Data: Listing 2.6.1

<DIRECTORY PATH>PROGRAM NAME Executed: DDMMMYYYY hh:mm

Table 1.6.11.4

Kaplan-Meier Analysis of Time to Onset of AE (Falls) by Age Safety Population

Repeat of 1.6.10.3

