- Figure 3.6.3.3 Kaplan-Meier Analysis of Time to Onset of AE (Hallucinations) by Age Safety Population
- Figure 3.6.3.4 Kaplan-Meier Analysis of Time to Onset of AE (Hallucinations) by Race Safety Population
- Figure 3.6.3.5 Kaplan-Meier Analysis of Time to Onset of AE (Hallucinations) by Baseline Renal Function Safety Population
- Figure 3.6.3.6 Kaplan-Meier Analysis of Time to Onset of AE (Hallucinations) by Weight Safety Population
- Figure 3.6.3.7 Kaplan-Meier Analysis of Time to Onset of AE (Hallucinations) by Baseline MAO-B Inhibitor Medications Safety Population
- Figure 3.6.3.8 Kaplan-Meier Analysis of Time to Onset of AE (Hallucinations) by Baseline Dopamine Agonist Medications Safety Population
- Figure 3.6.3.9 Kaplan-Meier Analysis of Time to Onset of AE (Hallucinations) by Baseline Levodopa Dose Safety Population
- Figure 3.6.3.10 Kaplan-Meier Analysis of Time to Onset of AE (Hallucinations) by Time since PD Diagnosis in Years Safety Population
- Figure 3.6.3.11 Kaplan-Meier Analysis of Time to Onset of AE (Hallucinations) by Age at PD Diagnosis Safety Population
- Figure 3.6.3.12 Kaplan-Meier Analysis of Time to Onset of AE (Hallucinations) by Prior Deep Brain Stimulation Safety Population
- Figure 3.6.3.13 Kaplan-Meier Analysis of Time to Onset of AE (Hallucinations) by Geographic Region Safety Population

Figure 3.1
Kaplan-Meier Analysis of Time to Study Drug Discontinuation
Safety Population

[figure not shown]

Analysis Day is the number of days since Analysis Day 1 + 1. Subjects will be censored if study drug was not discontinued at or before the last contact. Source Data: Listing 2.1.3, Table 1.1.3

<DIRECTORY PATH>PROGRAM NAME Executed: DDMONYYYY HH:MM

Programming note: All treatment/analysis groups will be presented.

 $\mbox{Figure 3.6.1.1} \\ \mbox{Kaplan-Meier Analysis of Time to Onset of AE (Neuropsychiatric)} \\ \mbox{Safety Population}$

[figure not shown]
The Neuropsychiatric category combines the following System Organ Classes: Nervous system disorder and Psychiatric disorder. Analysis Day is the number of days since Analysis Day 1 + 1. Subjects will be censored at their last contact date if no AE (Neuropsychiatric) occurred. Source Data: Listing 2.6.1, Table 1.6.10.2

<DIRECTORY PATH>PROGRAM NAME Executed: DDMONYYYY HH:MM

Programming note: Only Placebo and 340mg ADS-5102 will be presented.

[figure not shown]

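### The three special-interest incidence tables (SAP 1.6.10.1, 1.6.11.1, 1.6.12.1) print event counts with no N, subjects or percentages, contrary to SAP 9.2, and no other table gives combined-category subject incidence for ≥340 mg and ADS-5102

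*SAP*

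**What the plan says.** SAP 9.2 sets the counting rule: "For each summary, at each of the SOC and PT levels, a subject will be counted once if he/she reported one or more AEs". It sets the denominator too: "Percentages will be calculated out of the number of subjects in the Safety population". SAP Section 6 has the same general rule: "Categorical data will be summarized by the number and percentage of subjects in each category".

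SAP 9.2.8 defines three special-interest categories. The neuropsychiatric category merges two system organ classes (SOCs). Falls and hallucinations each merge every preferred term (PT) containing the relevant word. For the incidence display it says only "Event incidence will be summarized treatment/analysis group", with no counting unit, no denominator and no exception to 9.2.

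The shell for Table 1.6.10.1 has "Number of AE (Neuropsychiatric) events" as its top row. Every cell, down to PT level, is a single number, and the column heads carry no N. Tables 1.6.11.1 (falls) and 1.6.12.1 (hallucinations) are each specified as "Repeat of 1.6.10.1". Their footnotes nevertheless state "Percentages are calculated out of the number of subjects in each treatment group" and go on to describe censoring.

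Two other groups of tables bear on the same events:

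- The Kaplan-Meier tables (1.6.10.2, 1.6.11.2, 1.6.12.2) give N and the number (%) of subjects with a first event in the category, for two columns. The matching figure shell says "Programming note: Only Placebo and 340mg ADS-5102 will be presented".
- Table 1.6.2.1 gives N and subject n (%) by SOC and PT in all four columns.

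**The concern.** The SAP itself selected these three risks for special attention in an integrated safety summary that supports a submission. A programmer who follows the shells will produce tables titled as incidence that contain none.

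A raw count mixes three things: how many subjects the column holds, how long they were followed, and how often the same subject had the event again. The columns differ widely on the first two. A reader could take a several-fold difference in counts as a drug effect when the underlying rates are equal, and could not recover a risk per subject from the table. The text and shells also give the programmer conflicting instructions, and the footnotes under two of the tables describe statistics that the layout does not hold.

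**Working it through.** The documents state no figure on this point, so there is nothing to reproduce. The check compares text with shells and then shows by arithmetic how far raw counts could diverge.

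**1. Is this a conversion artefact?** No. Neighbouring shells (1.6.2.1, 1.6.5, 1.6.10.2) keep N in the heads and n (%) in the cells, and the row label itself names events.

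**2. Inputs**

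- AM201 (SAP Section 3): 83 subjects, 1:1:1:1, 8 weeks. 83/4 = 20.75, so assume 21 on placebo and 62 on the three active arms, 21 of them on 340 mg.
- PD301 (SAP Section 3): 126 subjects, 1:1, 25 weeks, so 63 per arm.
- PD302: up to 250 subjects, all active (Protocol 6.2, 6.3), for up to 101 weeks (Protocol 6.6). It is analysed at a database freeze (SAP Section 4) whose date and accrued exposure are not given. Assume a mean of 26 or 52 weeks.
- Full planned dosing in AM201 and PD301.

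**3. Ratio of counts at an equal event rate** (a common rate cancels, so the ratio is that of person-weeks)

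- Placebo: 21 × 8 + 63 × 25 = 168 + 1,575 = 1,743 person-weeks.
- ADS-5102, earlier studies: 62 × 8 + 63 × 25 = 496 + 1,575 = 2,071 person-weeks.
- 340 mg, earlier studies: 21 × 8 + 63 × 25 = 1,743 person-weeks.

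| PD302 assumption | ADS-5102 person-weeks | Ratio to placebo | 340 mg person-weeks | Ratio to placebo |
|---|---|---|---|---|
| 250 × 26 weeks | 2,071 + 6,500 = 8,571 | 4.9 | 8,243 | 4.7 |
| 250 × 52 weeks | 2,071 + 13,000 = 15,071 | 8.6 | 14,743 | 8.5 |
| 100 × 52 weeks | 2,071 + 5,200 = 7,271 | 4.2 | 6,943 | 4.0 |
| none | 2,071 | 1.2 | 1,743 | 1.0 |

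The ≥340 mg column lies between the other two. If all earlier-study active exposure is dropped, 250 × 26 / 1,743 is still 3.7.

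**4. Repeat events.** In a placebo column of 84 subjects, 20 falls could be 20 subjects (20/84 = 23.8%) or one subject (1/84 = 1.2%). The shell cannot tell these apart.

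**5. How much does n (%) repair?** It removes the column-size part. With 250 in PD302 and rollover overlap unknown, ADS-5102 N lies between 250 and 62 + 63 + 250 = 375, which is 3.0 to 4.5 times the 84 on placebo. Mean follow-up on placebo is 1,743/84 = 20.8 weeks. On ADS-5102 it is 8,571/375 = 22.9 to 8,571/250 = 34.3 weeks in the 26-week case (1.1 to 1.7 times placebo). In the 52-week case it is 15,071/375 = 40.2 to 15,071/250 = 60.3 weeks (1.9 to 2.9 times). That part remains after n (%) is added.

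**6. What is planned elsewhere**

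| Subject n (%) | Placebo | 340 mg | ≥340 mg | ADS-5102 |
|---|---|---|---|---|
| By SOC and PT (1.6.2.1) | yes | yes | yes | yes |
| By combined category (Kaplan-Meier tables) | yes | yes | no | no |

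The two empty cells cannot be filled by adding SOC or PT rows, because one subject may appear in several.

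**The case against.** A reader might infer that neuropsychiatric events, falls and hallucinations cannot be compared between columns at all. The documents do not support that. The Kaplan-Meier tables compare Placebo with 340 mg by category, with N, subject counts and allowance for censoring. Table 1.6.2.1 covers each SOC and PT in all four columns.

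The case for leaving the shells alone goes further:

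- The SAP does not rank its tables. An event count fits the loose wording of 9.2.8 and could be meant as a supplement. No formal testing is planned, so no inference rests on it.
- The two columns without category-level incidence add to the 340 mg column only the 260 mg and 420 mg arms of AM201: about 62 − 21 = 41 subjects for 8 weeks, or 328 person-weeks. That is 3.8% of 8,571 or 2.2% of 15,071.
- If only one PT qualifies for a category, its row in Table 1.6.2.1 already gives the missing figure. The documents do not list the PTs.
- Table 1.5 gives n and mean exposure for all four columns, from which a reader could approximate person-time.

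Most of this narrows the consequence, and it is right that the gap is small in subjects. It does not remove the conflict: 9.2 covers every summary, 9.2.8 makes no exception, and the tables are titled as incidence. The single-PT escape cannot apply to the neuropsychiatric category as defined over two SOCs. The Table 1.5 route is only approximate, because its note limits subjects with a treatment gap to their PD302 exposure.

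**Conclusion.** The point holds as an inconsistency between text and shells with a practical consequence. As drawn, the three tables breach 9.2 and on their own do not allow comparison across columns. At equal event rates the ADS-5102 count would be about 5 times placebo at a mean PD302 exposure of 26 weeks and about 9 times at 52 weeks. This assumes 250 enrolled and full planned dosing in AM201 and PD301. Lower enrolment or exposure at the freeze reduces it.

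A reader might also infer a 16-fold gap. That needs all 250 PD302 subjects to average the full 101 weeks: (2,071 + 250 × 101) / 1,743 = 27,321 / 1,743 = 15.7. It is an upper bound, not an expectation. PD302 enters at a freeze, and Protocol 13.1.1 aims for 100 subjects completing one year out of up to 250. Nor is the whole gap the cost of breaching 9.2, since the part due to longer follow-up would survive a switch to n (%).

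The remaining omission is narrow: subject incidence for the combined categories in the ≥340 mg and ADS-5102 columns. It should be corrected before the tables are programmed.

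**What to change.** Redraw Table 1.6.10.1, and through it 1.6.11.1 and 1.6.12.1, with N in each of the four column heads and n (%) of subjects with at least one event at category, SOC and PT level. This is what 9.2 requires, and it supplies the missing category-level figures for ≥340 mg and ADS-5102.

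Keep event counts only as a labelled secondary figure, preferably with events per 100 person-years. The rate is an improvement rather than a 9.2 requirement; it is worth having because n (%) does not adjust for unequal follow-up. The person-time rule for subjects with a treatment gap should be stated so that events and exposure cover the same period.

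Replace the Kaplan-Meier footnote text under 1.6.11.1 and 1.6.12.1 with a note on subject counting and the denominator, and state the counting unit in 9.2.8.

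The cost is three table shells, one sentence of SAP text and the existing adverse-event program. No new data are needed.
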